9.7.1.6.1 PRIMARY EFFICACY ANALYSIS

Primary analysis of primary endpoint

The primary analysis will be based on MCI/Prodromal subjects from the FAS with the prespecified censoring rule applied. The primary endpoint is the change from baseline to 18 months in the derived ADCOMS. The dose-response of the primary endpoint is modelled with a first-order normal dynamic linear model, where Normal and Inverse-Gamma priors are used. The primary efficacy analysis will calculate the Bayesian posterior probability that the dose identified is the most likely ED₉₀ dose that achieves 25% improvement over the placebo arm. At each interim analysis and the final analysis, 2 Bayesian probabilities will be summarized for each active dose: the probability it is the ED₉₀ dose and the probability of achieving 25% improvement over the placebo arm.

For the clinical efficacy data (ie, derived ADCOMS, MMSE, CDR, ADAS-cog, CBB, ISLT, and FAQ) subjects will be censored at the time of initiation of treatment with AChEIs or memantine, if they were not on these medications at the time of Baseline cognitive assessment (Visit 2), and will be censored at the time of dose adjustment of AChEIs or memantine if they were already on stable treatment with these medications at the time of Baseline cognitive assessment (Visit 2). The value of the primary endpoint for censored subjects will be imputed using data up to the censoring time and Bayesian longitudinal modeling.

Sensitivity analysis of primary endpoint

After unblinding, the primary endpoint will be analyzed using the Bayesian methods described above as well as conventional statistical methods. The following additional Bayesian analyses will be conducted as sensitivity analyses:

- The primary endpoint will be analyzed regardless of initiation of treatment, or dose adjustment, with AChEIs or memantine using the same Bayesian analysis method as primary analysis. This is an intent-to-treat analysis without any censoring.
- In case of early success, the primary analysis as well as the above sensitivity analyses will be repeated after all subjects have completed 18 months of treatment or have been lost to follow-up.

Statistical methods for the final conventional analyses will use a mixed-effects model with repeated measures (MMRM) on the change from baseline in the derived ADCOMS at 18 months. The model will include treatment groups, randomization stratification variables (the presence or absence of ongoing treatment with AChEIs or memantine or both, and *ApoE4* status), and baseline ADCOMS as covariates. Other covariates such as adjusted hippocampal volume will be studied. These analyses will be performed as sensitivity analyses on the FAS as well as the PP set and as such, no multiplicity adjustments will be made to account for the interim analyses. In case of early success, the conventional analyses will also be performed using the data collected before the interim analysis.

9.7.1.6.2 SECONDARY EFFICACY ANALYSES

The MCI/Prodromal Cohort

An MMRM will be used to analyze the following secondary endpoints:

- Change from baseline in total hippocampal atrophy at 12 and 18 months of treatment in MCI/Prodromal subjects as measured by vMRI
- Change from baseline in CSF $A\beta(1-x)$ after 4 weeks and 18 months of treatment in MCI/Prodromal subjects. Data from early discontinuations will also be included.

Comparisons between each treatment group and placebo will be performed.

The Mild to Moderate AD Cohort (revised per Amendment 01)

The MMRM will be used to analyze the change from baseline of derived ADCOMS at 18 months in mild to moderate AD. If there is no treatment group-by-population interaction in the overall study, the MMRM analysis will include all subjects (MCI/Prodromal or mild to moderate AD) in the overall study. Otherwise, the MMRM analysis will only include subjects in the Mild to Moderate AD cohort. The comparison between placebo and active doses will be performed within mild to moderate AD subjects regardless of subjects included in the MMRM analysis. Dunnett's method will be used to control for multiplicity due to multiple comparisons. (revised per Amendment 01)

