- Change from baseline in CSF A β (1-x) after 4 weeks and 18 months of treatment in MCI/Prodromal subjects. Data from early discontinuations will also be included.

Comparisons between each treatment group and placebo will be performed.

The Mild to Moderate AD Cohort (revised per Amendment 01)

An MMRM will be used to analyze the change from baseline of derived ADCOMS at 18 months in mild to moderate AD. If there is no treatment group-by-population interaction in the overall study, the MMRM analysis will include all subjects (MCI/Prodromal or mild to moderate AD) in the overall study. Otherwise, the MMRM analysis will only include subjects in the Mild to Moderate AD cohort. The comparison between placebo and active doses will be performed within mild to moderate AD subjects regardless of subjects included in the MMRM analysis. Dunnett's method will be used to control for multiplicity due to multiple comparisons. (revised per Amendment 01)

Analysis for exploratory endpoints

(revised per Amendment 01)

An MMRM will be used to analyze the following exploratory endpoints:

- Change from baseline in the derived ADCOMS at 12 months in MCI/Prodromal and mild to moderate AD subjects
- Change from baseline in total hippocampal atrophy at 12 and 18 months in mild to moderate AD subjects as measured by vMRI
- Change from baseline in CSF A β (1-42) after 4 weeks and 18 months in MCI/Prodromal subjects. Data from early discontinuations will also be included.
- Change from baseline in CSF A β (1-x) and CSF A β (1-42) after 4 weeks and 18 months in mild to moderate AD subjects. Data from early discontinuations will also be included.
- Change from baseline in the clinical assessments: ADAS-cog, CDR, MMSE, ISLT, CBB, and FAQ at 12 weeks and at 6, 9, 12, 15, 18, 19, and 21 months in MCI/Prodromal and mild to moderate AD subjects
- Change from baseline in plasma and CSF amyloid and CSF BACE1 measurements after 4 weeks and 18 months of treatment, and during posttreatment follow-up in MCI/Prodromal and mild to moderate AD subjects

- Change from baseline in left and right hippocampal, whole brain, and total ventricular volume at 6, 12 and 18 months as measured by vMRI in MCI/Prodromal and mild to moderate AD subjects

A linear mixed-model will be used to analyze the following exploratory endpoints:

- Change from baseline in brain amyloid levels as measured by amyloid PET at 18 months in MCI/Prodromal and mild to moderate AD subjects

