9.2.3 Rationale for the Use of Bayesian Adaptive Design

This study uses a Bayesian adaptive design for the MCI/Prodromal cohort only in Stage B. This design optimizes subject allocation and evaluation of efficacy in a smaller number of subjects by maximizing the number of subjects exposed to doses of interest. Frequent

interim analyses will be performed to assess the probability of early success and futility and to aid in making early stopping decisions. Response adaptive randomization will be used to update the randomization probability among treatment groups at each interim analysis, such that subjects are more likely to receive a dose that is efficacious.

Subjects with mild to moderate AD will be assessed as a “nested” population that does not follow the Bayesian adaptive design. It was not considered appropriate to have a Bayesian design for both cohorts as this would have substantially increased the overall study sample size, delayed analyses of dose response, and would have added background “noise” for the comparison of subjects with MCI/Prodromal AD compared with those with mild to moderate AD. Data from each cohort will be analyzed independently for the purposes of decision making. A separate analysis of the 2 cohorts avoids the risk of data from subjects with mild to moderate AD confounding the results for the primary population (MCI/prodromal). (revised per Amendment 01)

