The null and alternative hypotheses and the statistical test are the same as those for vMRI. To estimate the sample size for the amyloid PET imaging subgroup at 18 months, a common SD of the change from baseline was estimated at 0.33 and a reasonable mean difference between treatment and placebo was estimated as 0.25 (standardized uptake value ratio [SUVR]). Assuming a moderate dose-response, the best dose would achieve a difference of 0.25 (SUVR) and the middle and low doses would achieve a difference of 0.2 and 0.15 (SUVR), respectively; this would require a total of 100 subjects from all 4 arms at 18 months to achieve 80% power.

9.7.2.2 Sample Size Rationale for the Mild to Moderate AD Cohort (revised per Amendment 01)

ADCOMS at Month 18

The null hypothesis is that there is no difference between active dose and placebo. There are 2 null hypotheses corresponding to 2 active doses. The alternative hypothesis is that at least 1 null hypothesis is false. The null hypotheses will be tested using Dunnett's test with 2-sided alpha of 0.05 as described for the Mild to Moderate AD cohort in [Section 9.7.1.6.2](#). The statistical power was estimated through simulation for the dose-response assumption that the percent reduction in change from baseline of ADCOMS at 18 months compared with placebo would be 33% and 50% corresponding to the 2 doses, respectively. The estimated power for the actual planned 200 mild to moderate AD subjects is approximately 80% assuming a 2-sided alpha of 0.05. (revised per Amendment 01)

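### An undefined interaction judgement decides whether MCI/Prodromal subjects enter the Mild to Moderate AD analysis; this contradicts the stated independent analysis and leaves the 5% error rate unsecured

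*Protocol*

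**What the plan says.** Section 9.7.1.6.2, as revised per Amendment 01, sets the MMRM for 18-month ADCOMS in the Mild to Moderate AD cohort by a switch. One branch is "If there is no treatment group-by-population interaction in the overall study, the MMRM analysis will include all subjects (MCI/Prodromal or mild to moderate AD"). The other is "Otherwise, the MMRM analysis will only include subjects in the Mild to Moderate AD cohort". The Synopsis, under the analysis of secondary endpoints, repeats the rule: "If there is no treatment group-by-population interaction in the overall study, the MMRM analysis will include all subjects". Neither place names a test, a significance level or the model terms that define an interaction.

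The same paragraph then fixes the contrast, "The comparison between placebo and active doses will be performed within mild to moderate AD subjects regardless of subjects included in the MMRM analysis", and the multiplicity method, "Dunnett's method will be used to control for multiplicity due to multiple comparisons".

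Section 9.2.3 states: "Data from each cohort will be analyzed independently for the purposes of decision making". Its reason, in a sentence that ends by naming MCI/Prodromal as the group to be protected, is: "A separate analysis of the 2 cohorts avoids the risk of data from subjects with mild to moderate AD confounding the results for the primary".

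Section 9.7.2.2 powers the AD comparison on 200 AD subjects: "The null hypotheses will be tested using Dunnett's test with 2-sided alpha of 0.05 as described for the Mild to Moderate AD cohort". It assumes reductions of 33% and 50% at the two doses and gives power of approximately 80%. Sections 9.7.1.6 and 9.7.3 attach group-sequential efficacy boundaries to this comparison, with interim looks only after the MCI/Prodromal cohort has crossed its early success boundary.

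**The concern.** The AD comparison has its own Dunnett control, efficacy boundaries and power statement, so it is a decision analysis. Section 9.2.3 says such analyses are run separately by cohort. Section 9.7.1.6.2 instead lets the accumulated data choose between a model of about 200 subjects and one of up to 700.

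If the switch is run as a test, a non-significant result is weak evidence that the cohorts respond alike when one of them has only 200 subjects. What the pooled branch does to the AD error rate depends on two choices the protocol does not fix: whether treatment-by-population terms stay in the model, and whether each cohort has its own covariance matrix. At stake is whether a nominal 5% claim of efficacy in AD dementia really is a 5% claim.

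**Working it through.** **Inputs from the protocol.** 200 AD subjects at 1:1:1 (placebo, 15 mg, 50 mg); up to 500 MCI/Prodromal subjects over four arms; two-sided Dunnett at 0.05 for two doses; reductions of 33% and 50%.

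**Assumptions.** The protocol gives no SD, placebo change or AD dropout rate. I take 200/3 ≈ 66.7 AD subjects per arm (ignoring Stage A AD subjects on 5 mg) and 500/4 = 125 MCI subjects per arm (ignoring adaptive allocation). The interaction is a 2-df test on 15 mg and 50 mg at 5%. The Dunnett critical value is 2.212. The true AD effect is zero wherever error rates are quoted. Simulations used 200,000 to 400,000 replicates.

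**1. The plan's own power.** The standard error of an AD contrast is √(2/66.7) = 0.173 SD. Power is 37%, 70%, 79% and 91% at a placebo change/SD of 0.6, 0.9, 1.0 and 1.2. The stated 80% needs 1.02, or 1.14 with 20% dropout assumed. It is plausible but cannot be confirmed, and its stated basis is AD subjects only.

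**2. Pooled branch, AD-specific contrasts, cohort-specific covariances.** The AD estimate and its standard error then come essentially from AD data. Error stays near 5%, and the MCI effect cannot enter the contrast.

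**3. Pooled branch, AD-specific contrasts, one common covariance.** With r = AD SD / MCI SD, the variance used (in MCI units) is (500 + 200r²)/700 instead of r². The effective critical value is 2.212 × √[(500 + 200r²)/700] / r. For r = 1.25: (500 + 312.5)/700 = 1.161, whose square root is 1.077, and 2.212 × 1.077/1.25 = 1.91.

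That gives the error if the cohorts were pooled every time. The rule as written falls back to AD-only when an interaction is found, so it was simulated in full with MCI effects from 0 to 0.45 SD:

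| r (assumed) | variance used | effective critical value | error if always pooled | error under the rule |
|---|---|---|---|---|
| 0.8 | 0.897 | 2.62 | 1.7% | 2.3–3.8% |
| 1.0 | 1.000 | 2.21 | 5.0% | 5.0–5.2% |
| 1.15 | 1.092 | 2.01 | 8.1% | 6.6–7.3% |
| 1.25 | 1.161 | 1.91 | 10.2% | 7.4–8.8% |
| 1.5 | 1.357 | 1.72 | 15.2% | 9.4–11.8% |

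The last column describes the plan. For r above 1 its top value occurs with no MCI effect, because pooling is then most frequent. A larger MCI effect brings it down: at r = 1.5, from 11.8% to 9.4%.

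**4. Pooled branch, interaction terms dropped.** The MCI share of the common effect is 125/(125 + 66.7) = 65%. With equal SDs and the same MCI slowing at both doses:

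| MCI slowing | 25% | 35% | 45% |
|---|---|---|---|
| False-positive AD claim, placebo change/SD 0.6 | 18% | 28% | 38% |
| False-positive AD claim, placebo change/SD 1.0 | 35% | 45% | 40% |
| Trials pooled, placebo change/SD 1.0 | 79% | 63% | 43% |

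At 1.0 the rate falls again at 45% slowing because the interaction is detected more often.

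**5. AD-only MMRM with Dunnett.** Simulated error is 5.1–5.4% whatever the MCI effect. The slight excess comes from using a normal critical value with estimated variances.

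**The case against.** The strongest reply is the protocol's own sentence requiring the placebo comparison to be made within AD subjects whoever is in the model. A model with one common treatment effect offers no such contrast, so the text points to AD-specific contrasts, and step 4 is the disfavoured reading. That stands. A reader might infer that the rule would declare the drug effective in AD because it works in MCI, and that confining AD interim looks to the period after MCI success makes this worse. The documents do not support either inference: both need the interaction terms to be dropped. With AD-specific contrasts the MCI effect cannot bias the AD estimate.

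It can also be said that covariance structure and the interaction test are detail for the statistical analysis plan, to which Section 9.7.1 defers; that no document figure shows AD to be more variable than MCI, and the test is conservative if it is less variable; that the reason given in Section 9.2.3 protects only the MCI result, whose primary analysis is indeed not pooled; and that crossing an AD boundary is described as an early efficacy signal with no stopping action attached. These points limit the size and severity of the problem.

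They do not remove it. The protocol itself fixes the data-dependent switch, and the independence sentence covers each cohort, not only MCI. If the analysis plan kept separate terms and covariances throughout, pooling would share little beyond covariate estimates, and the switch would have little purpose.

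**Conclusion.** The concern holds as an internal contradiction plus an underspecified pooled model. Section 9.7.1.6.2 and the Synopsis conflict with Section 9.2.3 and with the 200-subject power basis in Section 9.7.2.2.

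A wrong error rate is possible but not established. It is about 5% with cohort-specific terms and covariances, or with equal SDs. Under a common covariance it is roughly 2–4% to 9–12% across assumed SD ratios of 0.8 to 1.5. The 18–45% range belongs only to the disfavoured reading and also rests on the assumed placebo change/SD and MCI slowing. Fewer than 500 MCI subjects, as after early success, would lessen the MCI weight.

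Severity: should be fixed. This is one secondary endpoint in a Phase 2 proof-of-concept study whose intended registration support is for the MCI/Prodromal population.

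**What to change.** Delete the interaction-dependent switch from Section 9.7.1.6.2 and from the Synopsis. State that the MMRM in the AD cohort only, with Dunnett for 15 mg and 50 mg against placebo, is the decision analysis at the interim and final looks. Keep any pooled model as supportive, always with treatment-by-population-by-visit terms and a separate covariance matrix per cohort.

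Requiring those terms and covariances within the present rule would also hold the within-AD error near 5%, but Section 9.2.3 would still have to be reconciled with the pooling.

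The cost is a few sentences, carried through to the statistical analysis plan and best settled before any AD data are unblinded. If the cohorts are truly alike, a little precision is lost in covariate and variance estimates. The stated 80% already rests on the AD subjects alone.

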9.7.1.6.3 EXPLORATORY EFFICACY ANALYSES

(revised per Amendment 01)

An MMRM will be used to analyze the following exploratory endpoints:

- Change from baseline in the derived ADCOMS at 12 months in MCI/Prodromal and mild to moderate AD subjects
- Change from baseline in total hippocampal atrophy at 12 and 18 months in mild to moderate AD subjects as measured by vMRI
- Change from baseline in CSF A β (1-42) after 4 weeks and 18 months in MCI/Prodromal subjects. Data from early discontinuations will also be included.
- Change from baseline in CSF A β (1-x) and CSF A β (1-42) after 4 weeks and 18 months in mild to moderate AD subjects. Data from early discontinuations will also be included.
- Change from baseline in the clinical assessments: ADAS-cog, CDR, MMSE, ISLT, CBB, and FAQ at 12 weeks and at 6, 9, 12, 15, 18, 19, and 21 months in MCI/Prodromal and mild to moderate AD subjects
- Change from baseline in plasma and CSF amyloid and CSF BACE1 measurements after 4 weeks and 18 months of treatment, and during posttreatment follow-up in MCI/Prodromal and mild to moderate AD subjects
- Change from baseline in left and right hippocampal, whole brain, and total ventricular volume at 6, 12 and 18 months as measured by vMRI in MCI/Prodromal and mild to moderate AD subjects

A linear mixed-model will be used to analyze the following exploratory endpoints:

- Change from baseline in brain amyloid levels as measured by amyloid PET at 18 months in MCI/Prodromal and mild to moderate AD subjects
- Change from baseline in CSF biomarkers of neurodegeneration (eg, tau, p-tau) at 18 months of treatment in MCI/Prodromal and mild to moderate AD subjects

Data from early discontinuations will also be used as appropriate. Comparisons between each treatment group and placebo will be performed.

A linear mixed-model with repeated measures will be used to determine the relationship between the following endpoints:

- Change from baseline in the derived ADCOMS score and the change from baseline in biomarkers in CSF at 18 months in MCI/Prodromal and mild to moderate AD subjects
- Change from baseline in the derived ADCOMS score and change from baseline in imaging biomarkers (hippocampal, whole brain, and total ventricular volumes) at 12 and 18 months in MCI/Prodromal and mild to moderate AD subjects

ApoE status for heterozygous and homozygous E4 carriers will be included in the model to assess the effect of *ApoE* status in this relationship.

9.7.1.7 Pharmacokinetic, Pharmacodynamic, Pharmacogenomic, and Other Biomarker Analyses

9.7.1.7.1 PHARMACOKINETIC ANALYSES

The Safety Analysis Set will be used for individual E2609 concentration listings. The PK Analysis Set will be used for summaries of E2609 concentrations.

9.7.1.7.2 PHARMACODYNAMIC, PHARMACOGENOMIC, AND OTHER BIOMARKER ANALYSES

Pharmacodynamic, PGx, and other biomarker analyses may be performed and reported separately. Details of these analyses may be described in a separate statistical analysis plan. Please also refer to [Appendix 3](#).

Pharmacodynamic Analyses

The PD Analysis Set will be used for the summaries and analyses of PD biomarkers (CSF and plasma biomarkers, MRI endpoints). CSF A β (1-x), A β (1-42), t-tau, p-tau, and BACE1 will be assessed and data will be presented graphically. Baseline levels and changes in t-tau and p-tau will be correlated with changes in CSF A β (1-42), imaging markers, and *ApoE4* status.

Summary statistics for CSF biomarkers will be assessed for evidence of a dose relationship.

Pharmacokinetic and Pharmacodynamic Analyses

The PK/PD relationship between CSF biomarker levels and exposure to E2609 in CSF will be explored graphically and any emergent relationship will be explored through population PK/PD modeling. The PK/PD relationship between plasma PK parameters with other biomarkers may also be explored using similar methods.

Additionally, the relationship between plasma and CSF exposure to E2609 and the derived ADCOMS at 18 months, and the relationship between plasma and CSF exposure to E2609 and the change from baseline for 18 months in the ADAS-cog, the CDR, and the MMSE, will be explored graphically. Any emergent relationship will be explored through population PK/PD modeling.

Exposure-safety analyses may also be conducted.

Pharmacogenomic Analyses

Blood samples will be used to determine the *ApoE* genotype and the *NAT2* phenotype of subjects enrolled in this study. The genomic DNA samples may also be stored and used as

described in [Section 9.7.1.7.2](#). Details of PGx testing may be provided and reported separately.

9.7.1.8 Safety Analyses

Evaluations of safety will be performed on the Safety Analysis Set. The incidence of AEs (including changes from baseline in physical and neurological examinations, and dermatological assessments), out-of-normal-range laboratory safety test variables, abnormal ECG findings, out-of-range vital signs, suicidality (C-SSRS), and results of the sleep questionnaire, along with the change from baseline in laboratory safety test variables, ECGs, safety MRI, and vital sign measurements will be summarized by treatment group using descriptive statistics.

9.7.1.8.1 EXTENT OF EXPOSURE

The extent of exposure to study drug will be summarized as cumulative extent of exposure in 3-month intervals. The number and percent of subjects will be presented by treatment group. Duration of exposure will be summarized using descriptive statistics in 3-month intervals. The number and percent of subjects will be presented by treatment group.

